4.5.3.2 Urinalysis

Urinalysis is assessed, using dipsticks, at the same visits as biochemistry and hematology. Urinalysis results will be listed only.

4.5.4 Quality of Life in Childhood Epilepsy (2–18 Years)

The QOLCE is a parent-reported questionnaire that evaluates health related quality of life in children aged 2–18 years old. It contains 76 items with 16 subscales covering 7 domains of life function: Physical activities, social activities, cognition, emotional well-being, behavior, general health, and general quality of life.

All items in the questionnaire are rated on a 5-point or 6-point categorical scale. Based on the responses to the items in each domain, scores for 16 subscales are derived. The subscales are presented in [Table 3](#).

Table 3 QOLCE Subscales

Subscale	Item Domains	Items Used
Physical Restrictions	Physical Activities	3.1 (a to j)
Energy/Fatigue	Physical Activities	3.2 (a,b)
Attention/Concentration	Cognition	5.1 (a,d,e,f,g)
Memory	Cognition	5.1 (j,k,l,m,n,o)
Language	Cognition	5.1 (p,q,r,s,t,u,v,w)
Other Cognitive	Cognition	5.1 (b,c,h)
Depression	Emotional Well-Being	4.1 (a,d,e,l)
Anxiety	Emotional Well-Being	4.1 (b,g,j,n,o,p)
Control/Helplessness	Emotional Well-Being	4.1 (c,f,h,i)
Self-esteem	Emotional Well-Being	4.1 (k,m,q,r,s)
Social Interactions	Social Activities	6.1 (c,f,h)
Social Activities	Social Activities	6.1 (a,e) and 6.2
Stigma Item	Social Activities	6.1 (i)
Behavior	Behavior	7.1 (a,c,f,g,h,i,j,k,l,m,o,q,r,s,t)
General Health Item	General Health	8.1
Quality of Life Item	Quality of Life	9.1

Items within each subscale will be coded and linearly transformed, according to the methods of Sabaz et al ¹. **Error! Reference source not found.**, to a score of 0 to 100, where 0 represents the lowest or poorest category and 100 represents the highest level of functioning.

A subscale score is calculated for each subscale by computing the mean of the items within the subscale. An 'Overall Quality of Life Score' can be calculated by taking the mean of the subscale scores.

Individual items will be listed only. The subscale scores and the overall quality of life score, recorded at each visit, will be summarized, on a continuous scale, by indication. The change from baseline will also be included.

The individual responses will not be listed, only the derived information for each derived score will be listed.

4.5.5 Quality of Life in Epilepsy, Version 2 (19 Years and Above)

The QOLIE-31-P is a survey of health-related quality of life for adults with epilepsy. It comprises 38 questions about health and daily activities and also includes questions designed to evaluate how much distress the patient feels about problems and worries related to epilepsy. The QOLIE-31-P will be administered to patients aged 19 years or older. Should the patient be unable to complete the QOLIE-31-P independently, it is permissible for their caregiver to assist.

The questionnaire consists of the following 7 subscales: energy, mood, daily activities, cognition, medication effects, seizure worry, and overall quality of life. Each subscale consists of a number of questions in addition to a 'distress' item. The raw score for each question and the 'distress' item are converted to a 0-100 score according to the scoring manual ² **Error! Reference source not found.** (higher scores reflecting greater well-being). The converted scores for each question within the subscale are then used to calculate a final subscale weighted score (higher scores reflect better quality of life; lower ones, worse quality of life) as follows:

(Sum of converted scores for each question in the subscale ÷ Number of questions in the subscale) × 'distress' item converted score

The total score (ranging from 0 to 100) is then calculated as:

(Sum of all subscale weighted scores ÷ Sum of all subscale 'distress' item converted scores) × 100

Individual items will be listed only. The weighted subscale scores and the total score, recorded at each visit, will be summarized, on a continuous scale, by indication. The change from baseline will also be included.

The individual responses will not be listed, only the derived information for each derived score will be listed.

4.5.6 Vineland Adaptive Behavior Scales, Second Edition

The Vineland-II is an individually administered instrument for assessing adaptive behaviors and consists of 4 adaptive behavior domains and a maladaptive behavior domain. The details of each domain are presented in [Table 4](#).

Table 4 Content Description of the Vineland-II

Domains and Subdomains	Number of Items	Age Range (Years)	Content
Adaptive Behavior Domains			
Communication Domain	99	≥0	
Receptive	20	≥0	How the individual listens and pays attention, and what he or she understands
Expressive	54	≥0	What the individual says, how he or she uses words and sentences to gather and provide information
Written	25	≥3	What the individual understands about how letters make words, and what he or she reads and writes
Daily Living Skills Domain	109	≥0	
Personal	41	≥0	How the individual eats, dresses and practices personal hygiene
Domestic	24	≥1	What household tasks the individual performs
Community	44	≥1	How the individual uses time, money, the telephone, the computer and job skills
Socialization Domain	99	≥0	
Interpersonal Relationships	38	≥0	How the individual interacts with others
Play and Leisure Time	31	≥0	How the individual plays and uses leisure time
Coping Skills	30	≥1	How the individual demonstrates responsibility and sensitivity to others
Motor Skills Domain	76	≥0 to <7	
Gross	40	≥0 to <7	How the individual uses arms and legs for movement and coordination
Fine	36	≥0 to <7	How the individual uses hands and fingers to manipulate objects
Maladaptive Behavior Domain			
Maladaptive Behavior Index	36	≥3	A composite of Internalizing, Externalizing, and Other types of undesirable behavior that may interfere with the individual's adaptive functioning

Internalizing (Section A)	11	≥3	
Externalizing (Section B)	10	≥3	
Other (Section C)	15	≥3	
Maladaptive Behavior Critical Items	14	≥3	More severe maladaptive behaviors that may provide clinically important information

For each subdomain, a raw score is calculated based on the responses to the individual items within the subdomain. For the maladaptive behavior index, the raw score is the sum of the 3 subdomain raw scores. Using the raw score and the patients' age the following are obtained:

- v-Scale Score: a type of standard score scale (standardized by age) to describe an individual's relative level of functioning. Ranging from a score of 1 to 24.
- 90% CI for the v-Scale Score: a range of scores that has a certain likelihood of including the individual's true score.
- Adaptive Level: a means to describe an individual's performance using terms that are nearly universal (Low, Moderately Low, Adequate, Moderately High, High).
 - For the maladaptive behavior index and maladaptive behavior subdomains the adaptive levels are: Average, Elevated or Clinically Significant.
- Age Equivalent: the age at which the raw score is average. Not applicable for the maladaptive behavior index and maladaptive behavior subdomains.

For each adaptive behavior domain, the sum of the v-scale scores of the subdomains is used along with the patients' age to obtain the following:

- Standard Score (standardized by age). Ranging from a score of 20 to 160.
- 90% CI for the domain standard score.
- Percentile Rank: the percentage of people whom the individual outperformed in his or her age group.
- Adaptive Level (Low, Moderately Low, Adequate, Moderately High, High).
- Stanine: whole number score ranging from 1 to 9 and representing a specific range of percentile ranks.

An adaptive behavior composite can then be obtained using the sum of the adaptive behavior domain standard scores (excluding the motor skills domain for patients ≥ 7 years of age). The same derived information as the adaptive behavior domain is obtained for the adaptive behavior composite.

For the maladaptive behavior index, all items within each section must be answered for a raw score to be calculated. If any of the items are missing, then the maladaptive behavior index score will be missing.

For the adaptive behavior subdomains, the derivation of the raw score allows for up to 2 missing values or answers of "Don't Know" within the items used for scoring. If there are more than 2 missing values or answers of "Don't Know" then the raw score will not be calculated and the subdomain score, domain score and adaptive behavior composite score will be missing.

The adaptive levels corresponding to the v-scale scores and standard scores are presented in [Table 5](#).

Table 5 Adaptive Levels by v-Scale Scores and Standard Scores

Adaptive Level	v-Scale Score for Subdomains and Maladaptive Behavior Index	Standard Score for Domains and Adaptive Behavior Composite
Adaptive Behavior Domains		
Low	1 to 9	20 to 70
Moderately Low	10 to 12	71 to 85
Adequate	13 to 17	86 to 114
Moderately High	18 to 20	115 to 129
High	21 to 24	130 to 160
Maladaptive Behavior Domain		
Clinically Significant	21 to 24	
Elevated	18 to 20	
Average	1 to 17	

The v-scale score from the 11 adaptive behavior subdomains, 3 maladaptive behavior subdomains and the maladaptive behavior index, and the standard score from the 4 adaptive behavior domains and the adaptive behavior composite, recorded at each visit, will be summarized, on a continuous scale, by indication. The change from baseline will also be included.

Each adaptive level for adaptive behavior will be coded with a score from 1 to 5, where 1 = Low, and 5 = High. Each adaptive level for the maladaptive behavior index will be coded with a score from 1 to 3, where 1 = Clinically Significant, and 3 = Average.

The individual responses within each domain will not be listed, only the derived information for each subdomain and domain will be listed.

4.5.7 Cognitive Assessment Battery

The cognitive assessment battery will be administered at Day 1, Week 48 (Day 336), Week 76 (Day 532) and at end of treatment. The items are age specific and the age of the patient at entry is the age used when choosing the items to be given. Children and adults are to complete the battery as able. It is expected that a number of patients will only be able to complete part of the battery and some may not be able to complete it at all. Parents and/or caregivers are to complete certain items.

The battery items will only be administered to a sub-group of sites that have the expertise to conduct the test. Assessments are conducted by an experienced psychometrician.

A summary of the patient and parent measures are given in [Table 6](#).

Table 6 Neuropsychological Protocol for Epilepsy Patients Treated with Cannabidiol – Patient and Parent Measures

Category	Function	Measures	Age Range
Patient	Intelligence IQ	WPPSI-4 Vocabulary, Matrix Reasoning	2;6 - 5;11 years
		WASI-2 Vocabulary, Matrix Reasoning (Including Wechsler: 'Digit Span' subtest from WISC-4 and WAIS-4; 'Coding' subtest from WISC-4 & WAIS-4; 'Bug Search' from WPPSI-4)	6 - adult
	Attention/Executive Trail Making	Trail Making Test D-KEFS	9 - adult
	Language Naming Fluency	Expressive One-Word Picture Vocabulary Test-4th Ed	2 - adult
		NEPSY-2 Word Generation	2 - 5 years
		F-A-S and Animals	6 - adult
	Visual-Spatial VMI	Developmental Test of Visual Motor Integration-6	2 - adult
Fine Motor Speed Pegs	Purdue Pegboard	4 - adult	
Parent	Executive	Behavior Rating Inventory of Executive Function (Parent and Teacher)	3 - 21 years
	Attention	ADHD Checklist (Parent and Teacher)	All ages
	Mood/Anxiety	BASC-2 (Parent and Teacher)	3 - 21 years
	Free-form report	Behavior Report Form (Parent and Teacher)	All ages

The following patient measures will be summarized, on a continuous scale, by indication at each visit and including the change from baseline using the scored recorded on the CRF:

- Intelligence:
 - WPPSI-4 T score:
 - Receptive Vocabulary.
 - Matrix Reasoning.
 - Bug Search.
 - WASI-2 T score:
 - Vocabulary.
 - Matrix Reasoning.
 - WISC-4 and WAIS-4:
 - Coding scaled score.
 - Digit Span (Forward, Backward, Longest forward, Longest Backward).
- Attention/Executive:
 - DKEFS scaled scores.
- Language:

- Expressive One-Word Picture Vocabulary Test-4th Ed scaled score.
- NEPSY-2 Word Generation scaled score.
- Visual-Spatial:
 - Developmental Test of Visual Motor Integration-6 standard score.
- Fine Motor Speed:
 - Dominant hand, non-dominant hand and both hands Z scores.

The following parent measures will be summarized, on a continuous scale, by indication at each visit and including the change from baseline using the scored recorded on the CRF:

- Executive:
 - Behavior Rating Inventory of Executive Function T scores for indexes and composite.
- Mood/Anxiety:
 - BASC-2 T scores for composite scores.

The behavior report form will be summarized, on a categorical scale, by indication at each visit.

The ADHD checklist consists of 18 questions, questions 1 to 9 relate to inattention and questions 10 to 18 relate to hyperactivity. A derived Inattention and Hyperactivity score can be calculated by taking the sum of the corresponding question responses, where 0 = 'Not at all' and 3 = 'Very much' and dividing by 9. A combined score can also be calculated by taking the sum of the responses from questions 1 to 18 and dividing by 18. The Inattention, Hyperactivity and combined scores will be summarized, on a continuous scale, at each visit and by indication. The change from baseline (Section 4.1.1.1) will also be included.

4.5.8 Vital Signs, Other Physical Findings and Other Safety Data

4.5.8.1 Vital Signs

All vital signs measurements are taken in a sitting position after five minutes of rest.

Summaries for vital signs (systolic blood pressure, diastolic blood pressure, pulse rate, temperature and respiratory rate) will be presented for each vital sign parameter at each visit. Change from baseline to each post-baseline visit will also be presented.

Based on the criteria presented in Section 6, clinically significant changes from core study baseline in vital signs measurements and other defined flagged values will be identified at each visit. The number of patients with a clinically significant change from core study baseline will be summarized by parameter and visit. The number of patients with at least one post-baseline flagged vital sign parameter value will be summarized by parameter and flagged criteria.

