4 EXPERIMENTAL PLAN

4.1 Study Design

This is a multi-center, OLE study for patients with DS or LGS who have completed the double-blind, placebo-controlled, clinical studies of GWP42003-P (Core Studies). The study consists of a titration period and a maintenance period, followed by a 10-day taper period.

Titration Period: All patients will titrate up to 10–20 mg/kg/day GWP42003-P using a recommended titration schedule (see [APPENDIX 4](#)). It is advised that the Investigator considers monitoring hepatic function (alanine aminotransferase [ALT], aspartate aminotransferase [AST], total bilirubin [TBL] and international normalized ratio [INR] levels) during the titration period for patients taking concomitant AEDs that are known to be associated with hepatic injury or failure. To minimize any elevations in hepatic function markers the titration period can be extended and the dosage of a concomitant AED and/or GWP42003-P may be adjusted at the discretion of the Investigator. If there is intolerance during titration, the patient may be maintained on a dose below 10–20 mg/kg/day. A titration rate faster than recommended may be considered if there is an increase in seizures, following consultation with the GW medical monitor.

Maintenance Period: Patients will continue dosing at 10–20 mg/kg/day. However, Investigators may decrease the dose if the patient experiences intolerance, or increase the dose if required for better seizure control, until the optimal dose is found. The Investigator may schedule additional clinic visits to facilitate dose adjustments e.g., when increasing doses above 20 mg/kg/day. Patients whose dose has been decreased can have their dose increased again provided there is adequate tolerance. The maximum dose patients can receive will be 30 mg/kg/day (51 mg/kg/day is the maximum dose safely used in the USA EAP to date with a mean dose of 24 mg/kg/day [$n = 59$]). Dose increases above 20 mg/kg/day are recommended to be done slowly, with maximum increments of 2.5 mg/kg every 5–7 days. If seizure freedom is achieved with use of GWP42003-P during the study, the Investigator can consider reducing the dose of concomitant AEDs after consultation with the GW medical monitor.

Study Completion: The maximum duration of this OLE study will be 4 years (208 weeks after Visit 1).

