7.1 Treatment Assignment

As this is a single-group OLE study, all patients will receive GWP42003-P. Patients will not be informed of their allocated treatment group in the Core Study. Patients will retain the patient number allocated to them during the Core Study.

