4.4.4 Demographic Data and Baseline Characteristics

The following demographic data will be summarized:

- Age (years);
- Age group (2-5 years, 6-11 years, 12-17 years and 18-55 years);
- Sex;
- Race;
- Country;
- Region (US, Rest of the World);
- Weight at Visit 1 (kg);
- Height at Visit 1 (cm);
- Body mass index at Visit 1 (kg/m²).

Age will be calculated as:

$$(\text{Date of Visit 1} - \text{date of birth}) \div 365.25$$

The following baseline characteristics will be summarized by indication and overall:

- Number of AEDs a patient is currently taking.
- Number of patients taking clobazam (Yes, No).
- Number of patients taking valproic acid (Yes, No).
- Number of patients taking lamotrigine (Yes, No).
- Number of patients taking levetiracetam (Yes, No).
- Number of patients taking rufinamide (Yes, No).
- Number of patients taking topiramate (Yes, No).
- Number of patients taking felbamate (Yes, No).

The number of AEDs a patient is currently taking is based on the 'Concomitant antiepileptic medications' CRF page. Patients taking the same AED type, but where the AED were coded to different generic terms will be counted only once within the AED type. For example, valproate sodium, valproic acid, valproate semisodium and ergenyl chrono will all be counted as valproic acid and counted once under that term.

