4.5.1 General Approach

All endpoints will be summarized on the safety analysis set, unless specified otherwise. Endpoints will be summarized by indication including an appropriate overall summary, unless specified otherwise. Each individual endpoint section also describes any further categorization of the data above that described in this section.

Throughout this section, whenever change from baseline is referenced and the endpoint is non-seizure related the baseline that is used will be the core study baseline. Please refer to Section 4.5.9 for specific rules for the choice of baseline for seizure-related endpoints.

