7. ATTACHMENTS AND APPENDICES

Appendix 1 Adverse Events of Special Interest – Abuse Liability

Withdrawal	Drug withdrawal convulsions
	Drug withdrawal headache
	Drug withdrawal maintenance therapy
	Drug withdrawal syndrome
	Drug withdrawal syndrome neonatal
	Drug rehabilitation
	Rebound effect
	Steroid withdrawal syndrome
	Withdrawal arrhythmia
	Withdrawal syndrome
Drug abuse and dependence	Dopamine dysregulation syndrome
	Drug abuse
	Drug abuser
	Drug dependence
	Drug dependence, antepartum
	Drug dependence, postpartum
	Intentional drug misuse
	Intentional overdose
	Maternal use of illicit drugs
	Neonatal complications of substance abuse
	Polysubstance dependence
	Substance abuse
	Substance abuser
	Accidental overdose
	Dependence
	Disturbance in social behaviour
	Drug administered at inappropriate site
	Drug detoxification
	Drug diversion
	Drug level above therapeutic
	Drug level increased
	Drug screen
	Drug screen positive
	Drug tolerance
	Drug tolerance decreased
	Drug tolerance increased
	Medication overuse headache
	Narcotic bowel syndrome
	Needle track marks
	Overdose
	Prescribed overdose
	Prescription form tampering
	Substance use
	Substance-induced mood disorder
Substance-induced psychotic disorder	
Toxicity to various agents	

Appendix 2 Ranges for Clinically Significant Changes and Other Defined Flagged Values in Vital Signs

The range of values that will be used to identify clinically significant changes in vital signs parameters (See Section 4.5.8.1) are presented in Table 7.

Table 7 Ranges for Clinically Significant Changes in Vital Signs

Vital Sign	Range
Sitting Systolic BP	Change: < -20, > 20
Sitting Diastolic BP	Change: < -10, > 10
Pulse Rate	Change: < -15, > 15
Weight	Percent Change: $\leq -7, \geq 7$

Defined flagged values that will be used to identify low or high vital signs parameters (See Section 4.5.8.1) are presented in Table 8.

Table 8 Other Defined Flagged Values for Vital Signs

Vital Sign	Flag
Sitting Systolic BP	< 90, > 140, > 160
Sitting Diastolic BP	< 50, > 90, > 100
Pulse Rate	< 60, > 100
Temperature	> 38.0, < 36.0
Respiratory Rate	< 12, > 20

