Table 13.1.1	Summary of Laboratory Safety Parameters – Hematology	Safety Analysis Set
Table 13.1.2	Summary of Laboratory Safety Parameters – Biochemistry	Safety Analysis Set
Table 13.2.1	Shift Table for Hematology Laboratory Parameters – Based on Reference Ranges	Safety Analysis Set
Table 13.2.2	Shift Table for Biochemistry Laboratory Parameters – Based on Reference Ranges	Safety Analysis Set
Table 13.3.1	Shift Table for Hematology Laboratory Parameters – Based on Toxicity Limits	Safety Analysis Set
Table 13.3.2	Shift Table for Biochemistry Laboratory Parameters – Based on Toxicity Limits	Safety Analysis Set
Table 13.4	Incidence of Hy’s Law Cases	Safety Analysis Set
Table 14.1.1	Summary of Vital Signs	Safety Analysis Set
Table 14.1.2	Incidence of Clinically Significant Changes from Baseline for Vital Signs	Safety Analysis Set
Table 14.1.3	Incidence of Defined Flagged Vital Signs	Safety Analysis Set
Table 14.2.1	Summary of ECG Parameters	Safety Analysis Set
Table 14.2.2	Incidence of Defined Flagged ECG Parameter Values	Safety Analysis Set
Table 14.3	Summary of Patients with Inpatient Hospitalizations due to Epilepsy	Safety Analysis Set
Table 14.4.1	Summary of Children’s Columbia-Suicide Severity Rating Scale	Safety Analysis Set
Table 14.4.2	Summary of Children’s Columbia-Suicide Severity Rating Scale by Type	Safety Analysis Set
Table 14.5	Summary of Tanner Stages	Safety Analysis Set
Table 14.6	Summary of Menstruation Details	Safety Analysis Set
Table 14.7	Summary of Cannabis Withdrawal Scale (18 Years and Above)	Safety Analysis Set
Table 14.8	Summary of Pediatric Cannabinoid Withdrawal Scale (4–17 Years)	Safety Analysis Set
Table 14.9	Summary of Study Medication Use and Behavior Survey	Safety Analysis Set
Table 14.10.1	Summary of Supplemental Drug Accountability Form	Safety Analysis Set
Table 14.10.2	Summary of Supplemental Adverse Event Form	Safety Analysis Set
Table 14.10.3	Summary of Site Classification Form	Safety Analysis Set

Table 13 List of Listings

Listing Number	Title	Analysis Set
Listing 1.1.1	Patient Disposition – End of Treatment	Safety Analysis Set
Listing 1.1.2	Patient Disposition – End of Taper	Safety Analysis Set
Listing 1.2	Inclusion/Exclusion Criteria Not Met	Safety Analysis Set
Listing 1.3	Visit Dates	Safety Analysis Set
Listing 2.1.1	Important Protocol Deviations	All Randomized Patients
Listing 2.1.2	All Protocol Deviations	All Randomized Patients
Listing 2.2	Analysis Sets	All Randomized Patients

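### SAP Table 14.1.3 counts any post-baseline vital-sign flag, on one set of cut-offs for ages 2 to 55, so it cannot separate new abnormalities from baseline status, age mix or length of follow-up

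*SAP*

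**What the plan says.** - **Counting rule.** SAP 4.5.8.1: "The number of patients with at least one post-baseline flagged vital sign parameter value will be summarized by parameter and flagged criteria". The output is Table 14.1.3, "Incidence of Defined Flagged Vital Signs" (SAP Appendix 5).
- **Cut-offs.** SAP Appendix 2: "Defined flagged values that will be used to identify low or high vital signs parameters (See Section 4.5.8.1) are presented in Table 8". Table 8 lists systolic <90, >140, >160; diastolic <50, >90, >100; pulse <60, >100; temperature >38.0, <36.0; respiratory rate <12, >20. It has no age column.
- **Population.** SAP 4.4.4 uses four age groups: 2-5, 6-11, 12-17 and 18-55 years.
- **Stratification.** SAP 4.5.1: "Endpoints will be summarized by indication including an appropriate overall summary, unless specified otherwise". Section 4.5.8.1 adds no age split.
- **Endpoint.** SAP 3.3.1 lists vital signs among the primary safety measures, assessed as change relative to the pre-randomization Core baseline.
- **Companion outputs.** SAP 4.5.8.1 also plans summaries and change from baseline at each visit for all five parameters. Table 14.1.2 counts clinically significant changes from Core baseline by parameter and visit. The criteria for Table 14.1.2 are in Table 7, which covers systolic pressure, diastolic pressure, pulse and weight.
- **Control.** Protocol 7.1: "As this is a single-group OLE study, all patients will receive GWP42003-P".

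**The concern.** The endpoint is defined relative to Core baseline, but the flag count ignores baseline. A patient who was outside a cut-off before randomization and has not changed since is counted exactly like a patient with a new abnormality. Because a patient counts once if any reading is flagged, the percentage rises with the number of readings taken, and patients in this study differ widely in follow-up. Because the cut-offs are the same at every age, the percentage also depends on the age mix wherever the distribution of a vital sign differs by age. The table shows none of these three influences separately.

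The start of the counting window is also open. Baseline means Core baseline (SAP 4.1.1.1), and the text does not say whether a Visit 1 value counts as post-baseline. Visit 1 precedes OLE dosing, so on one reading a former placebo patient could be counted on a value taken before any GWP42003-P. The potential Hy's Law table in SAP 4.5.3.1 avoids this by counting from after Visit 1.

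At stake is whether a reader can use this table as evidence for or against a vital-sign signal. That matters most for temperature and respiratory rate, which have no other categorical summary.

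**Working it through.** The plan gives no expected flag rate, age mix or sample size derivation, so there is no figure to reproduce. The arithmetic below only illustrates how the counting rule behaves.

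**Inputs from the documents.** The protocol's Appendix 1 schedules vital signs at Visits 2 to 12, End of Treatment and End of Taper: 11 + 1 + 1 = 13 assessments after Visit 1. SAP Table 2 labels 9 (Day 15, 29, 85; Week 24, 38, 48, 76; End of Treatment; End of Taper). A patient who withdraws after Visit 3 and tapers has 4 (Visits 2 and 3, End of Treatment, End of Taper).

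**Assumptions, not in the documents.** Per-visit probability p of a flag on one criterion: 1% to 50%. Within-patient correlation ρ: 0, 0.2, 0.4. No drug effect unless stated.

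**Formula.** With ρ = 0, P(at least one flag in k) = 1 − (1 − p)^k. With ρ > 0, beta-binomial: a = p(1 − ρ)/ρ, b = (1 − p)(1 − ρ)/ρ, and P = 1 − B(a, b + k)/B(a, b).

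**Step 1: number of assessments.** For p = 5% and ρ = 0, 1 − 0.95^13 = 48.7%. For ρ = 0.4, a = 0.075 and b = 1.425, which gives 17.9% at k = 13.

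| p = 5% | k = 4 | k = 9 | k = 13 | p doubled to 10%, k = 4 |
|---|---|---|---|---|
| ρ = 0 | 18.5% | 37.0% | 48.7% | 34.4% |
| ρ = 0.2 | 14.4% | 22.8% | 27.0% | 27.1% |
| ρ = 0.4 | 11.3% | 15.8% | 17.9% | 21.7% |

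At k = 13 the range over ρ is 3.8% to 12.2% for p = 1% and 56.1% to 94.5% for p = 20%. The last column shows what doubling p would do at 4 assessments. Going from 4 to 13 assessments has a larger effect than that doubling at ρ = 0, about the same at ρ = 0.2, and a smaller one at ρ = 0.4.

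**Step 2: baseline status.** With k = 13, the share of ever-flagged patients who were already flagged at baseline is 1 − [(1 − p) − P(no flag in 14)]/P(at least one in 13). For p = 5%, 20%, 50% this is 25.5%, 34.0%, 55.1% at ρ = 0.4 and 15.4%, 25.6%, 51.0% at ρ = 0.2.

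**Step 3: age.** With an assumed pulse SD of 12, ρ = 0.4 and k = 13, the percentage ever above 100 is 7.0% at an assumed mean of 75, 34.6% at 85, 76.7% at 95 and 96.2% at 105. The documents do not link any of these means to an age group. The step shows only that a fixed cut-off is sensitive to the group mean.

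**Step 4: what each part of a remedy does.** Among patients unflagged at baseline, the ever-flagged percentage at k = 13 and ρ = 0.4 is 14.1%, 46.3%, 80.7% for p = 5%, 20%, 50%, against 17.9%, 56.1%, 89.8% under the present rule. Conditioning on baseline therefore leaves most of the visit-count effect. A by-visit count removes it: for a patient unflagged at baseline, the chance of a flag at any one visit is a/(a + b + 1) = p(1 − ρ), which is 5%, 4%, 3% for p = 5% and ρ = 0, 0.2, 0.4, however long the schedule.

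**The case against.** The strongest case against is that baseline is already used where it matters. Section 4.5.8.1 plans change from baseline at each visit for every parameter, Table 14.1.2 counts significant changes by visit, and patient-level listings follow. Table 8 is headed "Other Defined Flagged Values for Vital Signs", which marks it as a supplementary screen. Low and high flags and the higher blood-pressure tiers are reported as separate rows. In a single-group study with no hypothesis testing, no vital-sign table can isolate a drug effect. All of this stands, and it confines the point to Table 14.1.3. It does not fill the gap for temperature and respiratory rate, which are absent from Table 7.

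Three stronger readings are tempting, and the documents support none of them.

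- A reader might infer that Table 14.1.3 reflects age and visit count more than drug effect. That needs flag rates, the age mix and an expected effect, and none is given. In Step 1 the visit-count comparison goes either way with ρ.
- A reader might infer that most young children will be flagged by design. No age-specific vital-sign values appear in either document.
- A reader might take the independent-visit figure of 49% as the expected size. If flags persist within a patient because of age or baseline status, ρ is high and extra visits add less. Thirteen readings also require the full 208-week schedule plus a taper visit, and patients who move to commercial product have no taper period.

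It is also fair to say that restricting the count to patients unflagged at baseline would hide those who were persistently flagged. They therefore need their own row.

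**Conclusion.** The point holds for Table 14.1.3 only. As written, the rule mixes new flags with flags present at Core baseline, pools ages 2 to 55 on fixed cut-offs, and lets the percentage grow with the number of assessments. The table therefore cannot separate these influences from a treatment-related change. These facts follow from SAP 4.5.8.1 and Appendix 2 and need no assumption.

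The size is not known. The 18% to 49% for 13 assessments (16% to 37% for the 9 in SAP Table 2) rests on an assumed 5% per-visit rate, no drug effect, and ρ from 0.4 to 0.

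The SAP already applies each of the missing principles elsewhere. The Hy's Law rule and the laboratory shift tables condition on Core baseline (4.5.3.1). Lymphocyte limits differ below and above 18 years (Appendix 4). Percentages for time of first AE onset are based on patients with a visit or call in each period (4.5.2). This is a cheap improvement to one safety table, not a defect in the vital-sign analysis as a whole.

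**What to change.** Amend SAP 4.5.8.1 and the specification of Table 14.1.3:

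1. For each criterion, count flags after Visit 1 among patients not flagged on that criterion at Core baseline.
2. Show patients flagged at Core baseline in a separate row.
3. Present the table by the four age groups of SAP 4.4.4, within indication and overall.
4. Add by-visit counts with the number assessed at that visit as denominator. The baseline condition does not remove the visit-count effect, so this step is needed as well.
5. Keep the existing Table 8 cut-offs.
6. Correct the pointer in 4.5.8.1. It sends the reader to Section 6, which is the reference list, whereas the criteria are in Appendix 2.

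The cost is SAP wording and programming on data already collected. The table becomes longer, and denominators will be small in some age groups.
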